2. determine the incidence of severe intraoperative adverse events;
3. determine the association between preoperative, intraoperative, and infrastructural factors and postoperative complications and death.

Methods

Study design

14-day Latin American international multicenter prospective cohort study of pediatric patients (<18 years) undergoing surgery.

Inclusion criteria

All of the consecutive patients under 18-years-old who were admitted to participating hospitals during the study period and who underwent elective and nonelective surgeries will be included in the study. This analysis will include outpatient surgeries and surgical procedures outside of operating rooms requiring local or general anesthesia. Recruitment will occur for fourteen days, starting on the date chosen by each participating hospital within the study cohort period (to be determined).

Exclusion criteria

1. patients undergoing radiological or other procedures that do not require general anesthesia or in which general anesthesia is performed but no procedure is performed (e.g., general anesthesia during MRI);
2. patients undergoing obstetric surgery.

Hospitals

Our goal is to recruit as many Latin American hospitals as possible. Each hospital will receive an individual report that compares its dataset with that of the overall national cohort.

Ethics in research and informed consent

Research ethics and regulatory approvals will be sought before the initiation of the study in each location by using national research legislation/guidelines for that country.

National leaders will ensure that the necessary ethical and regulatory approvals are obtained for participating hospitals in their country. Hospitals can only record data if there is ethical approval or an equivalent waiver.

This study is a large-scale clinical audit; therefore, it does not pose a significant risk to the study population. In most, if not all, countries, there will be no requirement for individual patient consent, as all of the data will be anonymized and are expected to be recorded as part of routine clinical practice.

A precedent has already been set from an international perspective. In the original EuSOS study, consent was provided in 27 of the 28 participating European countries. (13) In the ASOS study (12) and the ASOS-2 trial, consent was provided in most hospitals. In African pediatric perioperative studies, written informed consent was provided by six of eight ethics committees in the SAPSOS

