Each hospital will maintain a secure trial file, including a protocol, local investigator delegation record, ethics approval documentation, participant list, and other documentation (such as trial definitions).

A printout of the final summary of the included patients with essential variables should be produced for each hospital, along with the submission of final data for double-checking for completeness and accuracy.

Dataset

A realistic dataset will be critical to the success of the investigation, and this requirement was confirmed in the EuSOS (13), SASOS (14), and SAPSOS (5) studies, wherein almost complete data were available on the patients. Based on the SAPSOS and ASOS-Paeds study, we plan to adopt this dataset with minor changes to remove data that are deemed to be redundant to develop a simple, lean, and pragmatic dataset. We believe this simple dataset will encourage hospitals to participate.

Hospital-specific data will be collected once, including hospital level of care (primary, secondary, and tertiary), number of operating rooms, number of specialists, number and level of intensive care beds, equipment suitable for pediatric surgery and anesthesia, availability of drugs and blood products, details of hospital reimbursement status, and holidays or other local factors that affect patient flow during the study period.

Case registration forms

A CRF LASOS-Peds will be completed for each eligible patient who undergoes surgery during the cohort period. Patients will be followed up until hospital discharge. This will be censored in thirty days; specifically, patients will be followed up until discharge or for thirty days after surgery if they are still in the hospital.

Sample size calculation

We plan to recruit as many hospitals from each participating country as possible and ask them to include all eligible patients in the study. We do not have a specific sample size, and statistical models will be adapted to the event rate provided by the recruited sample to avoid inappropriate use of any logistic regression models.

Statistical analysis

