The data to be collected are all collected as part of routine clinical care. Categorical variables will be described as proportions and compared by using chi-square tests. Continuous variables will be described as the mean and standard deviation if normally distributed or as the median and interquartile range if not normally distributed. The univariate analysis will test factors associated with postoperative complications, intensive care admission, and in-hospital death.

Hierarchical multilevel logistic regression models will be constructed to identify factors that are independently associated with these outcomes and to adjust for differences in confounding factors. Factors will be entered into the models based on their univariate relationship with the outcome ($p < 0.05$), biological plausibility, and low rate of missing data. Logistic regression results will be reported as adjusted odds ratios (ORs) with 95% confidence intervals. Moreover, models will be evaluated by using sensitivity analyses to explore

possible interacting factors and to examine any effect on the results. A statistical analysis plan will be written before the analysis.

Primary outcome

Postoperative complications in the hospital up to 30 days after surgery.

Secondary outcomes

1. Mortality on the day of surgery;
2. Hospital mortality up to 30 days after surgery;
3. Risk factors associated with in-hospital complications;
4. Severe intraoperative critical adverse events;
5. Level of qualification of anesthesia and surgery providers, as well as the number of specialists per pediatric population;
6. Admission to intensive care.

Study organization and management

Study steering committee

The Steering Committee will be chaired by the leading researcher. The study management team will be appointed by the Steering Committee and led by the principal investigator. This team's duties will include the following:

- administration of all project tasks;
- communication between project partners (including funders, Steering Committee members, and national and local coordinators);
- data collection and management;
- preparation of reports to project sites;
- individual study.

The Steering Committee is responsible for the scientific conduct and consistency of the project. The Steering Committee will ensure communication between the funder(s), the trial management team, and coordinators, as needed.

National coordinators

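### Chi-square tests and the univariate p < 0.05 screen make no allowance for hospital clustering, so unadjusted p-values for hospital-level factors will be too small

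*Protocol*

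**What the plan says.** The Statistical analysis section of the protocol fixes three steps.

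- Unadjusted comparison: "Categorical variables will be described as proportions and compared by using chi-square tests".
- Univariate screen: "The univariate analysis will test factors associated with postoperative complications, intensive care admission, and in-hospital death". The test for this step is not named.
- Models: "Hierarchical multilevel logistic regression models will be constructed to identify factors that are independently associated with these outcomes". On selection, "Factors will be entered into the models based on their univariate relationship with the outcome" at p < 0.05, together with biological plausibility and a low rate of missing data. The levels of the hierarchy are not named.

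Three other places bear on these steps.

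- Secondary objective 3 is to "determine the association between preoperative, intraoperative, and infrastructural factors and postoperative complications and death".
- The Dataset section says "Hospital-specific data will be collected once, including hospital level of care (primary, secondary, and tertiary), number of operating rooms, number of specialists", and goes on to intensive care beds, equipment, drugs and blood products, and reimbursement status.
- Under Inclusion criteria, all consecutive eligible children in a participating hospital are taken: "Recruitment will occur for fourteen days, starting on the date chosen by each participating hospital within the study cohort period".

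The Summary gives 10,000 participants. The Sample size calculation section says that no specific sample size is set. Neither the number of hospitals nor an ICC appears anywhere.

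**The concern.** The design samples whole hospitals. A factor such as level of care has one value per hospital, so the number of independent observations on it is the number of hospitals. The ordinary chi-square test takes every child as independent. If complication rates differ between hospitals for reasons unrelated to the factor, the test reads part of that variation as an effect of the factor.

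The protocol itself expects clustering, because it plans hierarchical models for the adjusted analysis. The unadjusted tests that come before those models, and that help decide what goes into them, carry no such allowance.

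Two things are at stake. Unadjusted p-values reported for infrastructural factors would overstate the evidence. Hospital-level factors with no effect would also pass the p < 0.05 criterion too often and take up places in the models. That matters most for death, where events may be few and the protocol itself wants to avoid inappropriate use of logistic regression.

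**Working it through.** The plan states no figure that could be reproduced here, so the check is of how the stated test behaves under this design.

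**Inputs from the protocol**
- Total N = 10,000 (Summary).
- Nominal level 0.05 (Statistical analysis).
- Factor constant within hospital (Dataset).

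**Assumptions, because the protocol is silent**
- Number of hospitals H from 50 to 400, so mean cluster size m = 10,000/H runs from 200 to 25.
- ICC on the observed (0/1) scale from 0.005 to 0.10.
- Equal hospital sizes (coefficient of variation CV = 0), or CV = 1 for strongly unequal sizes.

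**Formulas**
- Design effect: DE = 1 + (m(1 + CV²) − 1) × ICC.
- True type I error of the nominal two-sided 5% chi-square: 2[1 − Φ(1.96/√DE)].

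**200 hospitals, m = 50, equal sizes**
- ICC 0.01: DE = 1 + 49 × 0.01 = 1.49; 1.96/√1.49 = 1.61; error 0.11.
- ICC 0.05: DE = 1 + 49 × 0.05 = 3.45; 1.96/√3.45 = 1.06; error 0.29.
- ICC 0.10: DE = 1 + 49 × 0.10 = 5.90; 1.96/√5.90 = 0.81; error 0.42.

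**Ends of the range**
- Mildest: 400 hospitals, m = 25, ICC 0.005, equal sizes. DE = 1 + 24 × 0.005 = 1.12; error 0.064.
- Most severe: 50 hospitals, m = 200, ICC 0.10, CV = 1. DE = 1 + (400 − 1) × 0.10 = 40.9; error 0.76.

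Unequal sizes make matters worse. With 200 hospitals, ICC 0.05 and CV = 1, DE = 1 + (100 − 1) × 0.05 = 5.95 and the error is 0.42 instead of 0.29.

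**Check by simulation.** Beta-binomial data were simulated with 4,000 replicates, an assumed outcome rate of 10% and a null binary factor. For a hospital-level factor in 200 hospitals, the rejection rate was 0.106, 0.281 and 0.425 at ICC 0.01, 0.05 and 0.10, in agreement with the formula. For a patient-level factor split evenly within each hospital, the same chi-square rejected in 0.034 to 0.052 of data sets (100 and 200 hospitals, same ICCs). That is about nominal or slightly conservative.

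**Rarer outcome.** A separate simulation used a normal random hospital intercept, 200 hospitals of unequal size (mean 50) and death at an assumed 1%. It gave errors of 6%, 8% and 14% at latent-scale ICC 0.05, 0.10 and 0.20. At an assumed 10% complication rate the corresponding errors were 17%, 30% and 45%. The inflation is therefore much smaller for a rare outcome.

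**The case against.** The strongest reply is that the protocol's inference on risk factors comes from hierarchical multilevel models with adjusted odds ratios and 95% confidence intervals. A null hospital factor that slips through a loose screen must still face a test that allows for clustering. An over-permissive screen adds surplus covariates but does not by itself produce false adjusted findings. This stands, provided that hospital is a level. It is the natural level, but the protocol does not say so. The reply does not rescue the unadjusted p-values or the screen.

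Second, chi-square is not named as the test for the univariate screen, and a statistical analysis plan is promised that may specify another. That is also true. However, chi-square is the only test the section names before the models, and the univariate sentence follows in the same paragraph, so it is the natural reading. Even on the narrow reading, the stated chi-square comparisons remain wrong for categorical hospital-level factors.

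Third, model entry does not rest on the p-value alone: plausibility and missingness count too. This tempers the over-admission but does not remove it.

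Fourth, the chi-square sentence covers categorical variables only. Counts such as operating rooms or specialists fall under it only if they are grouped. This narrows the reach of the stated test. A patient-level test of any other kind on those counts would have the same fault.

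**Conclusion.** The point holds, at moderate severity. As written, the unadjusted comparisons and the p < 0.05 criterion ignore hospital clustering, and for factors constant within hospital the p-values are too small whenever the ICC is above zero. How much too small depends on figures that the protocol does not give. The true error is about 0.11 to 0.42 for 200 hospitals at ICC 0.01 to 0.10, and about 0.06 to 0.76 over the whole range examined.

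A reader might infer more than the document supports.

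- *That the p-values are grossly wrong in every case.* With many small hospitals and a low ICC, or for a rare outcome such as death, the inflation is mild.
- *That the adjusted odds ratios are invalid.* They come from multilevel models and are protected if hospital is a level.
- *That every chi-square test in the study fails.* For patient-level factors balanced within hospitals the test is close to nominal.
- *That the interval for the primary incidence will be too narrow.* The protocol states no method for that interval, so there is nothing there to correct.

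**What to change.** In the Statistical analysis section, for factors recorded at hospital level, replace the chi-square comparison and the univariate screen with single-factor logistic models that have a random hospital intercept. GEE or Rao-Scott tests with hospital as the cluster are an acceptable alternative. State that hospital is a level in the hierarchical models. Chi-square may stay for patient-level factors that are reasonably balanced within hospitals, although using the same single-factor multilevel model throughout would be simpler to describe.

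The cost is a change of wording in the protocol and the analysis plan, slightly more analysis work, and larger unadjusted p-values for hospital-level factors. No new data are required, because every patient record is already collected by hospital.
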